### Exclusion criteria

### Rationale

- |   |   |
|---|---|
| 
23. Facial skin and/or lipoatrophy other than age-related, due to medical conditions (e.g., congenital defect, trauma), or abnormalities in adipose tissue related to immune-mediated diseases, such as generalized lipodystrophy (e.g., juvenile dermatomyositis), partial lipodystrophy (e.g., Barraquer-Simons-Syndrome), inherited disease or HIV-related disease.
 
24. A propensity towards pigmentary skin changes such as hyper- or hypopigmentation in the face, inflammatory skin conditions, keloid formation, or hypertrophic scarring.
 
25. History or documented evidence of an autoimmune disease (e.g., scleroderma, lupus erythematosus, rheumatoid arthritis).
 
26. History of recurrent herpetic eruption in the facial region.
 
27. Systemic disorders which cause poor wound healing or will lead to tissue deterioration over the treated areas.
 
28. Present or uncontrolled malignant disease.
 
29. Any medical condition with the potential to interfere with the study or compromise subject safety, or increase the risk of AEs (e.g., epilepsy, impaired cardiac conditions, severely impaired hepatic function, severe renal dysfunction, porphyria, severe psychic, neurological or mental disease, current or history of drug or alcohol abuse, general infection).
 
30. Pregnant, breast-feeding women, or women who are of childbearing potential and not practicing a reliable method of birth control.
 
31. Subject who is imprisoned or is lawfully kept in an institution.
 
32. Employee or direct relative of an employee of the CRO, the study site, or Merz.
 
33. Participation in a clinical study within the last 4 weeks prior to Day 1 and in parallel to this investigation.
 
34. Previous participation in this clinical study.
 | 
Safety concern
 
Administrative
 
Administrative
 
Administrative
 
Administrative
 |
|---|---|

Exclusion criteria 12, 17, and 30 must be confirmed at V2 if touch-up treatment is planned.

 - confidential -	Merz Pharmaceuticals GmbH	M900391005/RaLido
	Clinical Protocol for post market clinical follow-up studies (PMCF)	

*In case that any of the exclusion criteria, e.g., history or presence of a disease, disorder, allergy, etc. might be unknown or questionable, the subject should not be included in the study until the respective exclusion criterion has been clarified.*

## **7.4 Removal of subjects from treatment or assessment**

### **7.4.1 Discontinuation of subjects**

In accordance with the Declaration of Helsinki and the informed consent form, the subject may discontinue the study at any time without any penalty or loss of benefits to which the subject is otherwise entitled (see Section 7.4.3). Both the discontinuation of study and the reason(s) why the study was prematurely discontinued must be recorded in the subject file and the eCRF. Date and discontinuation circumstances should be stated.

Subjects must be discontinued from the study by the investigator at any time for any of the following reasons:

- Withdrawal of informed consent.
- Pregnancy (no further administration of SMD will be performed).
- Any AEs for which treatment continuation would constitute an unacceptably high risk for the subject.
- Subject is lost to follow-up.

Clinical protocol deviations or conditions arising from the exclusion criteria established in Section 7.3, may (but will not necessarily) lead to the subject's discontinuation. All such conditions should be properly documented.

Subjects who are discontinued from the study due to AEs will be treated according to standard clinical strategies and will be followed-up until the final study visit/safety visit as described in Section 10. All pertinent information concerning the AE will be documented in the subject file as well as in the eCRF AE report form.

In case of study discontinuation of a subject the final study visit according to Table 7 should be performed for safety reasons. The investigator is required to make every effort to contact subjects lost to follow-up, and all such efforts should be documented in the subject file (e.g., times and dates of TC, copies of letters). Discontinued subjects will not be replaced.

 - confidential -	Merz Pharmaceuticals GmbH	M900391005/RaLido
	Clinical Protocol for post market clinical follow-up studies (PMCF)	Version 1.0 18-Jun-2018

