## 6.2 Discussion of study design, including choice of control groups

The prospective, open label multicenter PMCF study design was chosen to adequately investigate the performance and safety of the SMD as per the current practice.

In general, prospective designs can achieve a higher data quality as compared to retrospective designs.

In order to collect “real-life” data, it has been decided not to interfere with investigators’ usual practice and therefore employ a PMCF design. This design will allow evaluation of performance and safety of the SMD while used as per its current approved IFU.

Using several study sites increases the representativeness of the study results and decreases study site-related biases.

The observational period of approximately 18 to 19 months (if touch-up has been performed) was chosen to allow assessment of late-onset reactions.

The volume of the SMD to be injected as well as the choice of the injection technique are at the discretion of the investigator. This reflects the common use of fillers among physicians because the volume is adapted to the depths and the size of the areas to be treated as well as to the quality/thickness of the skin in these areas. Moreover, it depends on the desired cosmetic outcome which is usually a collective decision of both the treating physician and the subject.

Investigators should use only the needles provided in the SMD packaging, however, investigators are allowed to use cannulas at their own choice instead of the supplied needles, if cannulas instead of needles are usually being used in their daily practice. As this is a PMCF study with the main focus on performance and safety under real life conditions in daily practice, a control group that will be left untreated is not foreseen.

A blinded rater at each study site not otherwise involved in study procedures was chosen to assess the primary endpoint. The blinded rater does not know which indications were treated, which helps minimize the possible effects of evaluator bias.

 - confidential -	Merz Pharmaceuticals GmbH	M900391005/RaLido
	Clinical Protocol for post market clinical follow-up studies (PMCF)	

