## 8.2 Treatments administered

The SMD will be applied according to the administration method and volumes described in the current IFU and in Section 8.2.2.

The treatment plan will consist of one injection session at Day 1 and an optional touch-up treatment after 4 weeks.

The following treatment order is recommended (depending on the indications the investigator considers for treatment):

- Progress from cranial to caudal (upper cheek augmentation before nasolabial folds and marionette lines).
- Nasolabial folds after upper cheek augmentation and before marionette lines.
- Marionette lines at the end.

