**Table 7: Overview of study activities/visit schedule**

MRZ 900391005	Base-line	Follow-up/ optional touch-up	TC Follow-up	Prim. endpoint visit	Optional prim. endpoint visit	Follow-up visits	Final study visit e
Visit	V1	V2	V2A b	V3 c,d	V3A c	V4 c,d and 5 c,d	V6 c,d,e Final study visit
Timepoint	Day 1	Week 4	Week 8	Week 12/16	Week 16	Weeks 24/28 and 48/52	Week 72/76
Visit window		± 7 days	± 7 days	± 7 days	± 7 days	± 14 days	± 14 days
Informed consent	X						
Inclusion/exclusion criteria	X						
Exclusion criteria N° 12, 17, 30		X b					
Demographics	X						
Relevant medical history/concomitant diseases	X						
Previous & concomitant medications/treatm.	X	X	X	X	X	X	X
Photographs	X						
Determination of treatment indications	X	X b					
iGAIS/sGAIS		X		X	X	X	X
MAS (blinded rater)	X a	X		X	X	X	X
MAS (treating invest.)	X a						
Injection/touch-up	X	X b					
██████████ ██████████ ██████████ ██████████	■	■					
AEs /SAEs	X	X	X	X	X	X	X
Device deficiencies, technical complaints	X	X					

a MAS of blinded rater needs to be confirmed by the treating investigator prior SMD application;

b in case of optional touch-up;

c for subjects with no touch-up, primary endpoint will be assessed at Week 12. For subjects with touch-up in all indications treated at Day 1, primary endpoint will be assessed at Week 16. For patients with partial touch-up (in at least one indication, but not in all indications treated at Day 1), the primary endpoint for the indications that did not receive touch-up will be

 - confidential -	Merz Pharmaceuticals GmbH M900391005/RaLido	
	Clinical Protocol for post market clinical follow-up studies (PMCF)	Version 1.0 18-Jun-2018

assessed at Week 12 and for the indications that received touch-up will be assessed during the additional visit V3A at Week 16, follow-up visits will occur at Weeks 28, 52, and 76;

- d if all indications treated at V1 are also treated at the optional touch-up, V3, 4, 5, and 6 will be at Weeks 16, 28, 52 and 76, respectively;
- e in case of premature study discontinuation a final study visit has to be performed for the subject.

 - confidential -	Merz Pharmaceuticals GmbH	M900391005/RaLido
	Clinical Protocol for post market clinical follow-up studies (PMCF)	

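### Protocol section 7.4.1 merges the end of device administration with the end of study participation, so later follow-up after pregnancy or an AE discontinuation is lost or not assured

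*Protocol*

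**What the plan says.** Protocol 7.4.1 sets the rule: "Subjects must be discontinued from the study by the investigator at any time for any of the following reasons". Four reasons follow. Consent withdrawal and loss to follow-up end data collection by their nature. The other two are worded in terms of dosing: "Pregnancy (no further administration of SMD will be performed") and "Any AEs for which treatment continuation would constitute an unacceptably high risk for the subject".

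Dosing is short. Protocol 8.2 states: "The treatment plan will consist of one injection session at Day 1 and an optional touch-up treatment after 4 weeks". Follow-up is long: the 18 to 19 months of observation "was chosen to allow assessment of late-onset reactions" (Protocol 6.2).

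On what happens after discontinuation, the protocol says several things:
- Section 7.4.1: subjects discontinued because of AEs "will be followed-up until the final study visit/safety visit as described in Section 10".
- Section 7.4.1, next paragraph: "In case of study discontinuation of a subject the final study visit according to Table 7 should be performed for safety reasons".
- Table 7, footnote e: "in case of premature study discontinuation a final study visit has to be performed for the subject".
- Section 9.5: further safety contact after that assessment is possible if judged necessary.
- Section 10.1.1: AE observation ends at the subject's last study visit; an observed AE is followed until resolved or explained; the final visit is placed at 72 or 76 weeks.
- Section 10.5: a pregnancy is followed to its outcome. Nothing continues the scheduled visits.

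**The concern.** A reason to give no more device is treated as a reason to leave the study. After the touch-up window there is no injection left to withhold, and Table 7 schedules only AE questions, concomitant therapies, blinded scale ratings and global improvement ratings. A subject who becomes pregnant at Month 6 must still leave.

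For AE cases the possible loss is selective. Subjects whose early reaction weighed against a second injection are selected on device tolerability. If their observation stops early, new late events among them are not systematically collected, and late-onset reactions are what the long follow-up is for. They stay in the safety evaluation set (Protocol 12.2), whose main result is overall incidence of treatment-emergent AEs (Protocol 12.4.2.1, SAP 7.2.1), with no exposure adjustment described. Late incidence would then be biased downward.

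There is a smaller cost for performance. A missing Week 12/16 response counts as non-response in the full analysis set (Protocol 12.4.4.1, SAP 7.1.1), and the subject drops out of the per protocol set (SAP 5), although a rating could have been made.

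**Working it through.** **1. Does follow-up continue after an AE discontinuation?** The provisions side by side:

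| Provision | Points to follow-up to Week 72/76 | Points to an early end |
|---|---|---|
| Protocol 7.4.1, AE sentence | Promises follow-up to a final study visit or safety visit under Section 10 | Section 10 defines no safety visit |
| Protocol 7.4.1, final-visit sentence; Table 7 footnote e | – | Final study visit is performed at premature discontinuation |
| Protocol 10.1.1 | Final visit placed at 72 or 76 weeks; known AEs followed until resolved or explained | AE observation ends at the subject's last study visit |
| Protocol 9.5 | Later telephone or clinic contact possible | Discretionary |
| Protocol 7.4.3 | – | Discontinued subjects return to their own physician |

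Follow-up of a known AE is provided for. Scheduled detection of new late events is not settled. For pregnancy, the left-hand column holds only the outcome follow-up in section 10.5.

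**2. The plan's safety figure.** Inputs from Protocol 12.1 and SAP 4: 175 treated and at least 161 completing per indication, AE incidence 1%.
- Planned loss: (175 − 161)/175 = 14/175 = 8.0%.
- Detection: 1 − 0.99^161 = 80.2%, matching the stated 80%. With 160 subjects it is 79.97%, so 161 is the smallest number that reaches 80%.

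**3. Effect on head count.** No discontinuation rate is given, so q is an assumption. If the losses fall within the planned 14, at least 161 complete and detection stays at 80.2% or more. If they come on top, completers = 161 − 175q, rounded down:

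| Assumed q | Completers | 1 − 0.99^n |
|---|---|---|
| 1% | 159 | 79.8% |
| 2% | 157 | 79.4% |
| 5% | 152 | 78.3% |
| 8% | 147 | 77.2% |

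**4. Effect of selective loss.** Illustration, all inputs assumed: late-event risk 1% in other subjects and RR × 1% in those discontinued, with every late event in the latter unrecorded (the early-end reading). True rate = 0.01(1 − q) + 0.01·RR·q; observed rate with all treated in the denominator = 0.01(1 − q). Share of late events missed = 1 − observed/true:

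| q | RR = 1 | RR = 5 | RR = 10 |
|---|---|---|---|
| 1% | 1.0% | 4.8% | 9.2% |
| 2% | 2.0% | 9.3% | 16.9% |
| 5% | 5.0% | 20.8% | 34.5% |

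For example, with q = 2% and RR = 5, the true rate is 0.0098 + 0.0010 = 1.08%, the observed rate 0.98%, and 9.3% of late events are missed.

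**5. Performance.** The plan's figures reproduce at n = 140: critical counts 99, 98 and 96 give powers of 89.6%, 92.6% and 96.6%, product 80.1%. At n = 175 the product is 93.2%. If a share q of subjects lacked the primary rating and the response rate became 0.75(1 − q), the product would be 88.7% at q = 1% and 82.3% at q = 2%. This is a worst case for any missing primary rating, not an estimate for this rule, because pregnancies or AEs after Week 16 cost no primary rating.

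**The case against.** A reader might infer that subjects with the worst early reactions are certain to lose the 18-month follow-up, leaving at about the touch-up visit with the course of their reaction cut off. The documents do not support that. Section 7.4.1 itself promises AE follow-up, section 10.1.1 follows observed AEs until resolved or explained, and sections 6.1 and 10.2.2 carry serious events further, including reporting of related serious events after the observation period. The early-end reading is open but not established, and it threatens new late events rather than the known one.

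Other points on that side also stand:
- The touch-up is optional (8.2.4), and conditions arising from the exclusion criteria need not lead to discontinuation (7.4.1). A subject with, say, injection-site inflammation may skip the touch-up and stay in. After the touch-up the AE trigger has no clear application.
- Section 6.2 explains the planned observation length; an exit rule for a few subjects sits badly with that aim but does not contradict it.
- Pregnancies should be few. With contraception failing in under 1% per year, and even if all 175 subjects in an indication were of childbearing potential, the bound over 72 weeks is 175 × 0.01 × 72/52 ≈ 2.4.
- Non-responder imputation works against the sponsor's claim, so it cannot inflate performance. Table 7 includes a scale rating at the exit visit, though not one at the Week 12/16 analysis visit.

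None of this cures the merged wording. Section 9.5 contact is discretionary, the safety visit is undefined, and pregnant subjects have no provision continuing their scheduled visits.

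**Conclusion.** The point holds as a wording defect with a safety-data consequence. Section 7.4.1 makes two dosing-related reasons into mandatory exits from a study whose dosing ends at about Week 4. For pregnancy, the loss of scheduled visits is plain from the text. For AE discontinuations, the text leaves open whether scheduled observation continues; known AEs are followed, new late events may not be collected.

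The number of subjects affected cannot be derived, since no rate is given and the 8% allowance is not split by reason. The detection probability moves by at most about 3 points even if an assumed 8% were lost on top of the plan, and not below 80% if the losses fall within it. The matter is therefore selective loss, not power. Its size depends on two unknowns: how many subjects are discontinued this way, and how much higher their late-event risk is. It is worth correcting because the change is cheap and bears on the stated purpose of the follow-up.

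**What to change.** Reconcile Protocol 7.4.1, 9.5, 10.1.1 and Table 7 footnote e so that they:
- distinguish the end of device administration from the end of data collection;
- leave the grounds for withholding the device as the sponsor has them;
- state that subjects who receive no further device continue the remaining Table 7 data collection (AEs, concomitant therapies, ratings) to Week 72/76, unless they withdraw consent or are lost to follow-up;
- say what the final study visit and the safety visit mean for a subject who does discontinue.

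Ratings obtained on schedule then enter the existing SAP analysis visits, so the SAP imputation rule need not change.

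The cost is a protocol wording change and a few more attended visits of a kind already in Table 7. Ratings taken during pregnancy may need a flag in the data.

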#### **7.4.2 Premature termination or suspension of the study or a study site**

The study or a study site can be prematurely terminated or suspended by the sponsor. Reasons for termination of the study or a study site may include, but are not limited to, the following:

- Subject enrollment is unsatisfactory.
- The risks and benefits of continuing the study have been reassessed, and the risks outweigh any potential benefits.
- In particular if an increase in the frequency or severity of expected AEs or newly identified harms, currently not regarded in the risk analysis, according to ISO 14971:2012 could have a significant impact on the benefit-risk analysis and which may lead to risks to the health or safety of subjects, users or other persons that are unacceptable when weighed against the intended benefits.
- New scientific data on the SMD do not justify a continuation of the study.
- The investigator or study site exhibit serious and/or persistent non-adherence to the CP, the Declaration of Helsinki, DIN EN ISO 14155:2012, and/or applicable regulatory requirements.
- The sponsor decides to terminate the study at any time for any other reason.

Furthermore, the study may be prematurely ended if the regulatory authority or the EC has decided to terminate or suspend approval for the study, the study site, or the investigator.

If the study is prematurely terminated or suspended for any reason, the investigator must inform the subjects and assure appropriate follow-up treatment. Within the timeframes noted in applicable regulations, the sponsor will promptly inform the investigators, study sites, the EC, and regulatory authorities of the termination or suspension of the study, as well as provide reasons for the action.

#### **7.4.3 Provision of care for subjects after study discontinuation**

After study discontinuation, the subjects will be treated by their physician according to their medical condition and standard treatments.

 - confidential -	Merz Pharmaceuticals GmbH	M900391005/RaLido
	Clinical Protocol for post market clinical follow-up studies (PMCF)	

## 8 TREATMENTS

### 8.1 Study medical device

The SMD RADIESSE® (+) Lidocaine is CE-marked in Europe since 02-JUN-2016 and will be injected as per its current approved labelling and investigator's usual practice.

#### 8.1.1 Description of study medical device

RADIESSE® (+) Lidocaine is a sterile, non-pyrogenic, semi-solid, cohesive implant. The principle component is synthetic CaHA suspended in a gel carrier that consists primarily of water (sterile water for injection USP), glycerin (USP), sodium carboxymethylcellulose (USP), and 0.3% lidocaine hydrochloride. The gel is dissipated in vivo and replaced with soft tissue growth, while the CaHA remains at the site of injection. The lidocaine provides short-term local anesthetic effect. The result is long-term yet non-permanent restoration and augmentation.

RADIESSE® (+) Lidocaine has a CaHA particle size range of 25-45 microns. It is indicated for plastic/reconstructive procedures, including deep dermal and subdermal soft tissue augmentation of the facial area and is also intended for restoration and correction of facial volume loss.

The SMD is provided sterile and non-pyrogenic in a syringe packaged in a foil pouch and boxed for convenient storage. Each syringe only unit consists of one pre-filled syringe containing 1.5 ml of RADIESSE® (+) Lidocaine and a Terumo K-Pack II with two 27 gauge thin wall injection needles.

##### 8.1.1.1 Instructions for preparation

The instructions for preparation of RADIESSE® (+) Lidocaine (e.g., the correct assembling of the needle to the syringe) are to be followed as described in the current version of the IFU. The treating investigator should check the integrity of the inner packaging and the expiry date for both the syringes and the needles prior to use. The products must not be used if the expiry date has lapsed or if the packaging has been opened or damaged or if the syringe end cap or syringe plunger is not intact.

##### 8.1.1.2 Instructions for administration

For successful treatment, it is essential that the treating investigator has experience with the injection techniques for treating nasolabial folds, marionette lines, and upper cheek

 - confidential -	Merz Pharmaceuticals GmbH	M900391005/RaLido
	Clinical Protocol for post market clinical follow-up studies (PMCF)	Version 1.0 18-Jun-2018

volume loss and has a deep knowledge of the facial anatomy. The treatment must be carried out under appropriate aseptic conditions.

The treating investigator determines the appropriate treatment area, depth, needle/cannula and injection technique based on clinical experience and preference in accordance with the current version of the IFU of the SMD. The SMD must be injected into a healthy, non-inflamed and previously rigorously disinfected skin. It should be injected into the deep dermal and/or subdermal soft tissue.

Injection volume of the SMD will be at the investigator's judgement based on subject's expectations, skin conditions and safety considerations and depends on the area to be treated and the extent of the volume loss/deficit. The optimal cosmetic outcome and an expected  $\geq 1$  point improvement on the respective MAS in each treated area should be achieved. However, over-correction should be avoided.

The SMD should be injected slowly with the least amount of pressure necessary. It should not be injected into blood vessels, into areas presenting cutaneous problems of an inflammatory or infectious type (e.g., acne, herpes) or into an area previously treated with a permanent dermal filler. For full exclusion criteria, please refer to Section 7.3. Only the nasolabial folds, the marionette lines, and the upper cheek should be treated, other regions of the face must not be treated in this study.

If the needle/cannula becomes obstructed during the procedure and the injection pressure is too high, the treating investigator should stop the injection and change the needle/cannula.

After injection of SMD, the treated area can be gently massaged to distribute the product uniformly.

The investigator will use the SMD and all study materials only within the framework of the clinical study and in accordance with this CP.

